10.6 Time to Death

From date of registration to date of death due to any cause. Patients last known to be alive are censored at date of last contact.

10.7 Pathologic Complete Response

No evidence of viable tumor cells on complete pathological evaluation of the surgical specimen per institutional standard of care.

11.0 STATISTICAL CONSIDERATIONS

11.1 Cohort A

a. Cohort A will use a single stage design with an accrual goal of 25 eligible patients in total. The anticipated accrual rate for Cohort A is 2 patients per month. Assuming an ineligibility rate of 20%, we will accrue 30 total patients to enroll 25 eligible patients.

b. Primary Endpoint:

The primary endpoint for Cohort A is pathologic complete response rate (pCR) as defined in Section 10.7. All patients who begin neoadjuvant therapy with pembrolizumab will be included in the analysis. Patients who are unable to have all sites of disease completely resected and patients who do not undergo surgery on protocol (for any reason) will be counted as non-responders.

This is a single stage design with the assumption that a true pCR of 25% or higher indicates that the treatment is of considerable interest for patients with resectable DM whereas a true pCR of 5% or lower indicates that the treatment will not be of further interest. Specifically, we will enroll 25 eligible patients with resectable DM. Four or more pathologic complete responses out of 25 would be considered evidence that the treatment warrants further study, provided other factors such as toxicity and overall survival also appear favorable. This design has an alpha of 3.4% (i.e. probability of declaring the regimen warrants further study when the true CR is 5%) and a power of 90% (probability of declaring the regimen warrants further study when the true pCR is 25%).

c. Secondary Endpoints

For the secondary endpoints, 25 eligible patients with measurable disease will be sufficient to estimate the overall response rate (ORR) at 9 weeks within ±19.6% (95% confidence interval). If only half of patients have measurable disease (13), then ORR can be estimated to within 27.2% (95% confidence Interval). Twenty-five eligible patients will also be sufficient to estimate the OS rate at a particular time point (e.g. 9 weeks) to within ±19.6% (95% confidence interval).

d. Other Objectives:

Toxicity will be assessed across all patients receiving pembrolizumab. With 25 patients, any toxicity with at least 5% chance of occurring has 72.3% chance of being observed at least once. For any toxicities, the study will estimate the rate of occurrence to within 19.6% (95% confidence interval).

To assess the hypothesis that higher mutational load is associated with pCR rate, the study will assess the association between overall mutational load and pCR rate. We will first calculate the per megabase mutation rate for each individual. Then we will use logistic regression to regress pCR status on the mutation rates and use a 1-degree freedom likelihood ratio test to obtain a p-value for the association between response and mutation rate. We will control the type I error at the two-sided alpha=0.05 level. We estimated the minimal detectable odds-ratio under the assumption that we will collect exome sequencing data on 25 patients and that we will control the type I error rate at the two-sided alpha=0.05 level. In prior data, the median number of mutations per megabase in desmoplastic melanoma was found to be 62 and the 25th and 75th percentiles were 33 and 101, respectively (private communication, [name] to [name], 11/18/2014). Therefore, by matching the quantiles, we approximate the distribution of the per megabase mutation rate across patients as a Weibull with shape parameter 1.4 and scale parameter 80. Assuming a baseline response rate of 5%, we anticipate over 80% power to detect a log odds-ratio of 0.31 (corresponding to an odds-ratio of 1.36) for each 10 mutation increase in the per megabase mutation rate. If logistic regression is unstable or behaves poorly, e.g. due to low response rates, we will also consider robust and flexible alternatives such as the Wilcoxon test to compare mutation rates between responders and nonresponders.

The study will examine whether change in T-cell infiltration following treatment is higher in the DM patients who respond. Specifically, we will compute the change in CD8 expression from baseline to resection and then compare the change between responders and non-responders using a two-sample t-test. We will control type I error at the alpha=0.05 level. Assuming that 25% of patients respond, then we anticipate 80% power to detect a difference in mean CD8 expression change 1.35 standard deviations. We will repeat the analysis comparing the change in CD8 expression from baseline to week 4 to determine whether T-cell infiltration in the on-treatment biopsy is associated with response at resection.

To assess the hypothesis that ctDNA fraction at baseline and week 4 are associated with response in DM patients, we will assess the association between response and ctDNA fraction using a two-sample t-test at the two-sided α =0.05 level. Assuming that 25% of patients respond, then we anticipate 80% power to detect a difference in mean ctDNA fraction of 1.35 standard deviations.

To assess the hypothesis that TCR clonality is higher in DM patients who respond, suggesting that the T-cells are targeting the tumor, we will compute the clonality metric as the normalized Shannon entropy for all patients at baseline, Week 4, and resection. We will then compute the change in clonality metric from baseline to resection. The change in clonality will be compared between responders and non-responders using a two-sample t-test with significance determined at the two-sided alpha=0.05 level. Assuming that 25% of patients respond, then we anticipate 80% power to detect a difference in clonality change of 1.35 standard deviations. We will repeat the analysis comparing the change in clonality from baseline to week 4 to determine whether T-cell clonality in the on-treatment biopsy is associated with response at resection.

The study will examine adaptive immune resistance by first evaluating whether PD-L1 expression is increased at Week 4 and resection as compared to baseline using paired t-tests and controlling the type I error at the two-sided alpha=0.05 level. With 25 patients, we anticipate 80% power at each time point to detect a mean difference in expression of 0.58 standard deviations. We will further evaluate whether increased PD-L1 expression at Week 4 or at resection is associated with response. Specifically, we will compute the change in expression from baseline to resection and then compare the change between responders and non-responders using a two-sample t-test. We will control type I error at the two-sided alpha=0.05 level. Assuming that 25% of patients respond then at each time point we anticipate 80% power to detect a difference in mean PD-L1 expression change of 1.35 standard deviations. We will repeat the analysis comparing the change in PD-L1 expression from baseline to week 4 to determine whether T-cell infiltration in the on-treatment biopsy is associated with response at resection. In addition to our assessment of overall mutational load, we will further conduct a neoantigen analysis. Specifically, we will predict the immunogenicity of each nonsynonymous somatic mutation using NetMHC. We will then use logistic regression to regress pCR status on the number of predicted immunogenic mutations, computing a pvalue using a 1-df test and controlling type I error at the two-sided alpha=0.05 level.

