14.0 DATA SUBMISSION SCHEDULE

14.1 Data Submission Requirement

Data must be submitted according to the protocol requirements for **ALL** patients registered, whether or not assigned treatment is administered, including patients deemed to be ineligible. Patients for whom documentation is inadequate to determine eligibility will generally be deemed ineligible.

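### Cohort A's pCR analysis includes every patient who starts pembrolizumab, but its go rule, alpha and power are set for 25 eligible patients (minor)

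*Combined protocol and SAP*

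**What the plan says.** Section 11.1a sets the size of Cohort A: "Cohort A will use a single stage design with an accrual goal of 25 eligible patients in total". It assumes 20% ineligibility, so "we will accrue 30 total patients to enroll 25 eligible patients".

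Section 11.1b defines who enters the pCR analysis: "All patients who begin neoadjuvant therapy with pembrolizumab will be included in the analysis". The next sentence begins "Patients who are unable to have all sites of disease completely resected and patients who do not undergo surgery on protocol" and counts these patients as non-responders. The go rule follows: "Four or more pathologic complete responses out of 25 would be considered evidence that the treatment warrants further study", subject to toxicity, overall survival and similar factors. The stated alpha is 3.4% at a true pCR of 5%, and the stated power is 90% at 25%.

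Three other places bear on the point:
- Section 11.1d, on toxicity: "Toxicity will be assessed across all patients receiving pembrolizumab". Its precision figures also use 25 patients.
- Section 14.1 requires data on every registered patient, "whether or not assigned treatment is administered, including patients deemed to be ineligible", and adds: "Patients for whom documentation is inadequate to determine eligibility will generally be deemed ineligible".
- Section 12.1 places the central review that standardizes pathologic eligibility after the study is complete.

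**The concern.** The analysis set is defined by starting treatment, while the rule and its error rates are defined by eligibility. The two coincide only if no ineligible patient is treated. The plan itself allows for ineligible registrations, and Sections 12.1 and 14.1 show how a patient could be found ineligible after treatment has begun. No cut-off is given for any denominator other than 25.

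The pCR count is the main input to the go decision. If treated ineligible patients are counted and the cut-off stays at 4, the rule is easier to pass than its stated alpha implies. Pathologic eligibility may also be decided when pCR results are already known, so the plan should fix beforehand which patients form the denominator.

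**Working it through.** **Inputs from Section 11.1:** 25 eligible patients, 30 accrued, cut-off 4, null pCR 5%, target pCR 25%.

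**Assumptions, not in the documents:** k treated ineligible patients are added to 25 eligible ones, and their pCR rate is (a) equal to, (b) half of, or (c) zero relative to the eligible rate.

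**Step 1: reproduce the plan's figures.** With X ~ Binomial(25, p), P(X ≥ 4) = 1 − [P(0) + P(1) + P(2) + P(3)].
- p = 0.05: 1 − (0.2774 + 0.3650 + 0.2305 + 0.0930) = 0.0341, the stated 3.4%.
- p = 0.25: 1 − (0.0008 + 0.0063 + 0.0251 + 0.0641) = 0.904 (unrounded 0.9038), the stated 90%.

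So the stated error rates belong to exactly 25 analysed patients.

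**Step 2: literal reading, cut-off kept at 4, equal pCR rate.** Now X ~ Binomial(25 + k, p). The larger set contains the eligible set, so the two readings disagree only when the larger set reaches 4 and the eligible set does not. The probability of disagreement is the difference between the two tails. For k=5 at p = 0.05 it is 0.0608 − 0.0341 = 0.0267.

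| k | n | Alpha | Power | Disagree at 5% | Disagree at 25% |
|---|---|---|---|---|---|
| 0 | 25 | 0.0341 | 0.9038 | 0 | 0 |
| 1 | 26 | 0.0387 | 0.9198 | 0.5% | 1.6% |
| 2 | 27 | 0.0437 | 0.9334 | 1.0% | 3.0% |
| 3 | 28 | 0.0491 | 0.9449 | 1.5% | 4.1% |
| 5 | 30 | 0.0608 | 0.9626 | 2.7% | 5.9% |

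The row k=5 is the upper case within the planned accrual: all 30 are treated and exactly 5 are ineligible.

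**Step 3: lower pCR rate in ineligible patients.** With Y ~ Binomial(k, p/2), P(X + Y ≥ 4), where X is the count among the 25 eligible, gives alpha/power of:
- k=1: 3.6%/91.2%
- k=3: 4.1%/92.6%
- k=5: 4.7%/93.8%

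If ineligible patients never respond, the values stay at 3.4%/90.4% for any k.

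**Step 4: other denominators.** At n=30, a cut-off of 5 would give alpha 1.6% and power 90.2%. At n=24 with a cut-off of 4 the values are 3.0%/88.5%. That case is realistic, because 20% ineligibility among 30 leaves 30 × 0.8 = 24 eligible.

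**The case against.** The best defence is context. The sentence after the all-treated statement makes patients without complete resection or surgery non-responders, so the evident purpose of the pair is to prevent exclusions after treatment starts. Section 11.1 repeatedly refers to 25 eligible patients, and the rule has one printed denominator and one printed cut-off. This makes the eligible-only reading likely, but no section states it. Section 11.1d does not settle it either, because it pairs all-treated wording for toxicity with calculations on 25.

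The second defence is size. Alpha stays below 5% for up to three treated ineligible patients, power only rises, and the plan sets no alpha ceiling for Cohort A that would be breached. The go decision also weighs toxicity and survival. All of this stands, and it is why the point is minor.

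The third defence concerns timing. Eligibility is affirmed before registration (Section 13.4b), with no exceptions allowed (Section 13.5). The central review uses slides from the primary diagnosis (Sections 12.1 and 15.2), not the resection specimen, and they are read as digital images with a redacted report, in batches during the study (Section 18.3). This lowers the risk that pCR influences eligibility. It does not remove it, since Section 12.1 puts the review after study completion and no section says that those settling eligibility are kept unaware of pCR.

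A reader might infer that Section 11.1b is silent on treated ineligible patients. It is not: on its face the sentence includes them. The difficulty is that the rule beside it was not calibrated for them.

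**Conclusion.** The concern holds as an inconsistency between the stated analysis set and the stated rule. Taken literally, the Cohort A rule no longer has 3.4% alpha and 90% power once a treated ineligible patient who could respond is counted.

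The size is modest. With equal response rates, alpha is 3.9% for one such patient and 4.9% for three. At half the rate it is 4.7% even for five. The number of treated ineligible patients and their pCR rate are assumptions; the 20% in Section 11.1a is an accrual allowance, and some ineligible patients may never start treatment.

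Two stronger conclusions might be drawn, and the documents support neither. One is that the design's true alpha is 6.1%: that needs all 30 treated, exactly five ineligible, an equal pCR rate in those five, and an unchanged cut-off. The other is that the denominator will be picked to suit the result: the plan leaves room for a late eligibility decision, but nothing indicates that one would be made with regard to pCR.

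Severity: minor.

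**What to change.** Make the decision set and the rule agree. Either option is sound, and the choice is the sponsor's:
- **Eligible treated patients.** Insert the word *eligible* in the analysis-set sentence of Section 11.1b. Keep 4 of 25 with 3.4% and 90%.
- **All treated patients.** Keep the sentence, and state the cut-off with exact alpha and power for each number that could be analysed. Step 4 shows why the cut-off must be named.

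With either option:
- Restate exact alpha and power if the number analysed is not 25.
- State that eligibility, including the central pathology review, is settled without knowledge of pCR.
- Report the other set as a sensitivity analysis.

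The cost is a few sentences in Section 11.1 and one in Section 12.1. No extra patients or data are needed. Under the first option the cut-off and the stated error rates at 25 do not change.

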To assess the hypothesis that higher mutational load is associated with CR rate, the study will assess the association between overall mutational load and CR rate. We will first calculate the per megabase mutation rate for each individual. Then we will use logistic regression to regress CR status on the mutation rates and use a 1-degree freedom likelihood ratio test to obtain a p-value for the association between response and mutation rate. We will control the type I error at the twosided alpha=0.05 level. We estimated the minimal detectable odds-ratio under the assumption that we will collect exome sequencing data on 21 patients and that we will control the type I error rate at the two-sided alpha=0.05 level. In prior data, the median number of mutations per megabase in desmoplastic melanoma was found to be 62 and the 25th and 75th percentiles were 33 and 101, respectively (private communication, [name] to [name], 11/18/2014). Therefore, by matching the quantiles, we approximate the distribution of the per megabase mutation rate across patients as a Weibull with shape parameter 1.4 and scale parameter 80. Assuming a baseline response rate of 5% we anticipate over 70% power to detect a log odds-ratio of 0.45 (corresponding to an odds-ratio of 1.57) for each 10 mutation increase in the per megabase mutation rate. If logistic regression is unstable or behaves poorly, e.g. due to low response rates, we will also consider robust and flexible alternatives such as the Wilcoxon test to compare mutation rates between responders and non-responders.

The study will examine whether change in T-cell infiltration following treatment is higher in the DM patients who respond. Specifically, we will compute the change in CD8 expression from baseline to progression and then compare the change between responders and non-responders using a two-sample t-test. We will control type I error at the alpha=0.05 level. Assuming that 20% of patients respond, then we anticipate 80% power to detect a difference in mean CD8 expression change 1.61 standard deviations. We will repeat the analysis comparing the change in CD8 expression from baseline to week 4 to determine whether T-cell infiltration in the on-treatment biopsy is associated with response at progression.

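### The mutational-load likelihood ratio test runs at about 7% in Cohort A and 7.5% in Cohort B, not the stated two-sided 5%

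*Combined protocol and SAP*

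**What the plan says.** Section 11.1d (Cohort A, Other Objectives) regresses pCR status on the per-megabase mutation rate by logistic regression and will "use a 1-degree freedom likelihood ratio test to obtain a p-value for the association between response and mutation rate". It adds: "We will control the type I error at the two-sided alpha=0.05 level". The planning rests on the "assumption that we will collect exome sequencing data on 25 patients". The covariate is modelled as a "Weibull with shape parameter 1.4 and scale parameter 80", matched to earlier data in which the median was "found to be 62 and the 25th and 75th percentiles were 33 and 101, respectively".

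Section 11.2d repeats this for Cohort B with CR as the outcome, on the "assumption that we will collect exome sequencing data on 21 patients".

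If the regression misbehaves, for instance because responses are few, "we will also consider robust and flexible alternatives such as the Wilcoxon test". The trigger is not defined, the list of alternatives is open, and the text does not say whether the alternative replaces the likelihood ratio test (LRT) or stands beside it.

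A separate neoantigen analysis will "regress pCR status on the number of predicted immunogenic mutations" (CR status in Cohort B). It uses a 1-df test whose type is not named.

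**The concern.** The chi-square(1) reference for an LRT is a large-sample approximation. At the design rates the plan expects 25 × 0.25 = 6.25 responders in Cohort A and 21 × 0.20 = 4.2 in Cohort B, with a right-skewed covariate. In that setting the approximation may give p-values that are too small.

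This is the formal test of objective 1.3a, which carries the trial's biological rationale. If its error exceeds the stated level, an association between mutational load and response would be claimed under the null more often than the protocol promises.

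**Working it through.** **Inputs.** n = 25 and 21; covariate Weibull(1.4, 80); two-sided alpha 0.05; design rates 25% pCR and 20% CR (Sections 11.1b, 11.2b). A 10% rate is added as an assumption to show the range.

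**What reproduces.** The Weibull quantile is 80 × (−ln(1−p))^(1/1.4). It gives 32.9, 61.6 and 101.0 at p = 0.25, 0.50 and 0.75, against the plan's 33, 62 and 101. The primary rules also reproduce: 3.4% / 90.4% for 4 of 25 and 8.5% / 82.1% for 3 of 21. The power statements hold as lower bounds if the 5% baseline is the response rate at zero mutations: about 88% for Cohort A and 95% for Cohort B.

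**Size of the planned test.** Draw X from the Weibull and Y independently of X. Fit the logistic model and compute LR = 2 × (maximised log-likelihood with slope − log-likelihood without slope). Reject if LR > 3.841. Under separation use the limiting LR; with no responders there is no test. The main runs had 60,000 null trials per setting, with Monte Carlo standard error √(0.05 × 0.95 / 60,000) = 0.09 point. The ranges below span separate simulations, some of them smaller.

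| Setting | Stated | Simulated |
|---|---|---|
| n=25, 25% | 5% | 6.6-7.0% |
| n=21, 20% | 5% | 7.4-7.7% |
| n=25, 10% | 5% | 7.6-7.8% |
| n=21, 10% | 5% | 8.0-8.4% |

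Across response rates from 5% to 50% the size stayed between 6.4% and 8.4%. With a single responder it was 11.7% (n=25) and 12.6% (n=21).

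**Size of the remedies.** Permuting response labels with the responder count fixed, on the observed covariates:
- ranked on the LRT statistic, 5.3% and 5.7% (n=25, 25%) and 5.3% and 4.6% (n=21, 20%), each from 1,500 trials with standard error about 0.6 point;
- ranked on the sum of mutation rates among responders, 5.1% and 4.8% (8,000 trials).

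The 1-df score test from the same model gave about 4.5-5.0% at rates of 10-25%.

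**Power**, permutation ranked on the sum:

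| Setting | LRT v chi-square | Permutation (sum) |
|---|---|---|
| A, log OR 0.31, overall pCR 25% | 86.3% | 86.1% |
| A, 5% at zero mutations | 88.6% | 88.1% |
| B, log OR 0.45, overall CR 20% | 90.4% | 89.2% |
| B, 5% at zero mutations | 95.7% | 93.5% |
| A, overall pCR 5% | 49.1% | 45.9% |
| B, overall CR 5% | 55.1% | 43.3% |

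The largest loss is 55.1 − 43.3 = 11.8 points.

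**Power if ranked on the LRT statistic.** These losses do not carry over. A check of 2,000 trials with 999 permutations gave 79.9% against 83.7% in Cohort A (overall pCR 25%) and 83.3% against 90.2% in Cohort B (overall CR 20%), losses of 3.8 and 6.9 points. With one responder this version cannot reject. The largest and the smallest covariate value both separate perfectly and tie, so the smallest p-value is 2/25 = 0.080 or 2/21 = 0.095. At an overall CR of 5%, the chance of at most one responder in 21 is 0.95^21 + 21 × 0.05 × 0.95^20 = 0.341 + 0.376 = 0.717. Power is then capped at 28%.

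**The case against.** The strongest reply is that the excess is 2-3 points on one exploratory p-value among many biomarker tests, each at an unadjusted 0.05, and that the plan already foresees trouble with few responders. The first part stands and limits the importance. The second is partly right: the 8% figure at a 10% rate assumes no fallback. At the design rates, however, replacing the LRT by exact Wilcoxon only on separation leaves 6.85% in Cohort A and 6.9% in Cohort B. Replacing it whenever there are fewer than five responders leaves 6.3% in Cohort A and brings Cohort B to 5.0%.

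A reader might infer that the Wilcoxon fallback raises the error further. The documents do not support that. The fallback is conditional on the regression misbehaving, and exact Wilcoxon is conservative here, so replacing the LRT lowers the error. Adding Wilcoxon only on separation changes nothing, and adding it only with few responders adds 0.3 point or less. Only an always-added rule in which either significant result counts raises it noticeably: 6.9% to 7.5% (n=25, 25%) and 7.4% to 7.8% (n=21, 20%). The plan does not state such a rule. What stands is that the fallback's trigger and role are unspecified.

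A reader might also extend the inflation to the neoantigen regressions. That is not shown: the 1-df test is not named and no distribution is given for the count. With the Weibull covariate as an illustration only, a Wald test runs at 1.9% and 1.0% and a score test at 4.9% and 4.7% (n=25 and n=21), none above 5%.

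**Conclusion.** The concern holds for the mutational-load LRT in both cohorts. Referred to chi-square(1), it does not deliver the stated 5%: the error is about 6.6-7.0% in Cohort A and 7.4-7.7% in Cohort B at the design rates. In Cohort B that is about one and a half times the stated level (7.5 / 5).

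This assumes that chi-square(1) is the intended reference, that the Weibull describes both cohorts, and that every planned patient has exome data. No response rate examined between 5% and 50% brings the LRT back to 5%.

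The finding does not reach the primary decision rules, which use response counts alone. Part of the LRT's apparent power advantage at very low response rates comes from its inflated error.

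**What to change.** In 11.1d and 11.2d, keep the logistic model but take the p-value from the permutation distribution of the LRT statistic on the observed covariates, with the number of responders fixed. This holds about 5% and stays valid under separation. Make it the single test of record and label Wilcoxon a sensitivity analysis, which removes the undefined switch. A 1-df score test from the same model is an acceptable alternative.

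Write down which statistic is ranked. Ranking on the sum of mutation rates among responders is equally valid and is the version to which the small power losses apply: about 0-2 points at the design rates, and up to about 12 in Cohort B if overall CR is 5%. Ranking on the LRT statistic cost about 4 and 7 points in the check above, and more with very few responders. The sum or the score test is therefore preferable if few responders are a real possibility.

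Using the same reference for the neoantigen regressions is for consistency only; at a minimum, name the 1-df test there. Apart from power, the cost is SAP wording and a few lines of code.
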